5.1 LABORATORY ASSESSMENTS

Laboratory assessments will be collected as specified in the study assessments and treatment schema and both Central and Local Laboratories will be utilized. Please refer to the lab manual for detailed instructions outlining procedures (ie- collection, preparation, shipping) for both local and central laboratories.

5.1.1 LOCAL LABORATORY ASSESSMENTS

1. Hematologic profile and serum chemistry to include:

Hematologic Profile		
Hematocrit	Neutrophils	Platelet count
Hemoglobin	Lymphocytes	Absolute lymphocyte count
Erythrocyte count	Monocytes	Leukocyte count
Basophils	Eosinophils	Absolute neutrophil count
Serum Chemistry		
Albumin	Glucose	SGOT [AST]
Alkaline phosphatase	GGT	SGPT [ALT]
Bicarbonate/CO ₂	LDH	Total bilirubin
BUN	Magnesium	Total protein
Creatinine	Phosphorus	Uric Acid
Chloride	Potassium	
Calcium	Sodium	

2. Serum and urine pregnancy test.
3. Coagulation lab tests to include PT and INR.
4. Cholesterol, LDL, HDL and Triglycerides will be done at timepoint specified in the Study Assessment table
5. Serum Virology to include HBsAG, HBc antibody, HCV antibody, and CMV IgG and IgM. If HBc antibody, HCV antibody or CMV are positive the subject must be evaluated for the presence of active HBV, HCV or active CMV IgM by DNA (PCR). CMV should be checked by PCR approximately every 3 cycles as part of the subject's scheduled visit. If subject is CMV positive, stop therapy and discuss intervention with medical monitor CMV surveillance will discontinue 30 days after last dose of umbralisib (EOT visit)..- See Appendix F.
6. Subjects with low-grade lymphoma should have a baseline bone marrow aspirate and/or biopsy prior to study entry, according to standard of care guidelines, and then to confirm CR. Bone marrow biopsy and aspirates should include FISH, flow cytometry and cytogenetics.

5.1.2 CENTRAL LABORATORY ASSESSMENTS

The following assessments will be shipped to and analyzed at a central laboratory. Please see Lab Manual for processing, handling, and shipping instructions.

5.1.2.1 LYMPHOCYTE SUBSETS

Peripheral blood for lymphocyte subsets will be drawn at the scheduled time points listed below.

LYMPHOCYTE SUBSET COLLECTION TIMES

Scheduled time point
Cycle 1 Day 1 (pre-dose)
Cycle 2 Day 1
Cycle 3 Day 1
Cycle 4 Day 1
Cycle 5 Day 1
Cycle 6 Day 1
Cycle 9 Day 1
Cycle 12 Day 1
Cycle 18 Day 1
Cycle 24 Day 1
End of Study

5.1.2.2 PHARMACOKINETIC BLOOD SAMPLES

PK blood (plasma) samples will be taken at the following timepoints during the dose-finding portion of the study. Additional PK samples may be collected outside of this schedule upon the occurrence of toxicity in order to correlate to plasma concentrations.

PHARMACOKINETIC COLLECTION TIMES

Visit	Scheduled time point
Cycle 1 Day 1	Pre-dose
Cycle 2 Day 1	Pre-dose
Cycle 3 Day 1	Pre-dose
Cycle 4 Day 1	Pre-dose
Cycle 5 Day 1	Pre-dose
Cycle 6 Day 1	Pre-dose

6 TREATMENT PLAN

6.1 TREATMENT SUMMARY

Treatment will be administered on an outpatient basis in 4-week (28 day) cycles.

UMBRALISIB (TGR-1202)

- 600 mg (safety run-in cohort) or 800 mg once daily through Cycle 24 (approximately 24 months). No additional umbralisib will be administered after Cycle 24.
- Subject diary will be utilized. Missed doses of umbralisib should be noted by the subject on the subject diary. In addition, drug accountability should be documented in the subjects medical record.

UBLITUXIMAB

- 900 mg Ublituximab on Days 1, 8, 15 of Cycle 1 and Day 1 of Cycles 2-6, Cycle 9 and 12. No additional ublituximab will be administered after Cycle 12.

6.2 AGENT ADMINISTRATION

6.2.1 GUIDELINES FOR ADMINISTRATION OF UMBRALISIB

- *Method of Administration:* Umbralisib will be administered orally once daily with food.
- *Potential Drug Interactions:* No drug interactions have been reported to date.
- *Pre-medications:* Subjects are required to start prophylaxis treatment for pneumocystis jiroveci pneumonia (PJP) as well as antiviral therapy prior to Cycle 1 Day 1.
 - *Anti-viral Prophylaxis:* Valtrex 500 mg daily or Acyclovir 400 mg BID or equivalent
 - *PJP Prophylaxis:* Dapsone 100 mg daily
- Final choice of PCP and anti-viral prophylaxis therapy is per investigator discretion.

NOTE: If PJP or anti-viral therapy is not tolerated, alternate to a different PJP or anti-viral therapy, discontinue, or reduce dose/schedule as per the discretion of the investigator.

Umbralisib will be dispensed at the sites by the research coordinator or designee under the direction of the PI or by a pharmacist at the site. Subjects must be provided drug in its original container. Subjects should be instructed to return any unused tablets when they return the bottle to the site. A drug diary should be provided to the subject. Study drug compliance should be reviewed with the subject at the beginning of each new treatment cycle and as needed. Missed doses will be documented in the subjects' medical record.

Umbralisib will be self-administered (by the subject). Tablets should be taken at approximately the same time each day with food (within 30 minutes of a meal). Subjects should be instructed to swallow the tablets whole and should not chew or crush them.

If a dose of umbralisib is missed, it should be taken as soon as possible on the same day. If it is

missed for a period of greater than 12 hours, it should not be replaced. If vomiting occurs, no attempt should be made to replace the vomited dose.

6.2.1.1 DISPENSING OF UMBRALISIB

Before dispensing, the site pharmacist or his/her representative must check that the umbralisib is in accordance with the product specifications and the validity is within the re-test date.

The pharmacist or his/her representative should record all umbralisib drug dispensations in the electronic drug accountability log. When doing this, the complete record should be logged. This includes the subject number, subject initials, date of dispensation, and lot number of the individual bottle.

The exact dose and the date of administration of umbralisib must be recorded within the eCRF and the subject's medical records. For the purpose of drug accountability and dosing, a drug diary will be utilized. Any error in drug administration should be recorded (e.g., missed dose) in the eCRF.

6.2.2 GUIDELINES FOR ADMINISTRATION OF UBLITUXIMAB

- *Method of Administration:* Ublituximab will be administered as an intravenous infusion through a dedicated line.
- *Potential Drug Interactions:* No drug interactions have been reported to date.
- *Pre-medications:* Ublituximab should be started approximately 30 minutes after the conclusion of the last pre-medication infusion and should include an antihistamine (diphenhydramine 50 mg or equivalent), and a corticosteroid (dexamethasone 10-20 mg or equivalent). If pre-medication is given orally, they should be given approximately 45-60 minutes prior to the beginning of the ublituximab infusion. If subject has a negative reaction to a premedication, change to an equivalent drug, decrease dose, or discontinue if subject cannot tolerate. Additionally, if subject has other health conditions that are adversely impacted by the premedication drug (s) consider changing drug/dose, or discontinuing if investigator feels it is in the subjects best interest.
 - Use of oral acetaminophen 650 mg (or equivalent) should be restricted to subjects who experience fever or pyrexia after week 1 dose, or as clinically warranted.
 - If after cycle 6, use of a corticosteroid is of clinical concern, please contact sponsor.
- *Hypersensitivity and Infusion Reaction Precautions:* Medication and resuscitation equipment must be available per institutional guidelines prior to ublituximab administration for the emergency management of potential anaphylactic reactions.
- *Subject Care Implications:*
 - Ublituximab should not be administered as an IV push or bolus.
 - Ublituximab may be administered on an outpatient basis.
 - Diluted ublituximab should be checked before administration for cloudiness, color, or deposits. Ublituximab should not be administered if does not conform to the

specifications. Immediately inform the Monitor/Sponsor with any product quality concerns or questions.

- It is recommended that ublituximab be administered immediately after dilution.
- No other treatment may be co-administered with ublituximab (other than for immediate intervention for adverse event).
- Concurrent glucocorticoid therapy as long as started for at least 7 days prior to study entry (\leq 10 mg per day of prednisone or equivalent) is allowed as clinically warranted.
- Since infusion-related hypotension may occur, **antihypertensive medications should be withheld 12-24 hours prior to and throughout infusion of ublituximab at investigator discretion.**
- For subjects at risk for tumor lysis syndrome in the opinion of the treating investigator, prophylaxis with allopurinol or per recommended institutional standards should be considered.

6.2.2.1 INFUSION RELATED REACTIONS AND INFUSION RATE GUIDANCE - UBLITUXIMAB

Infusion related reactions including severe reactions have been reported with ublituximab administration. Guidelines are provided below for subjects who experience such reactions. Symptomatic infusion reactions, despite premedication, may be treated at the discretion of the treating physician, including but not limited to: oral acetaminophen 650 mg (or equivalent), corticosteroids, antihistamines, oxygen, and bronchodilators.

The following are recommended infusion rate reduction/delay guidelines for subjects who experience severe Infusion Related Reactions (IRR's) in which treatment should be interrupted. Final decision for infusion rate reduction/delay or discontinuation resides with the treating investigator.

1st or 2nd Infusion Interruption:

- Hold infusion and closely monitored subject, institute symptomatic medical management until resolution of IRR symptoms.
- Following the judgment of the Investigator, and provided the subject is stable, the infusion may be resumed at no more than half the previous rate.
- If the subject does not experience any further IRR symptoms, infusion rate escalation may resume at the increments and intervals as appropriate at the treatment cycle dose (see Section 6.2.2.2).

3rd Infusion Interruption (same day):

- Discontinue infusion for that day – monitor subject for resolution of all symptoms. Subject should have all vital signs completed as well as any other standard of care procedures completed as warranted by the Investigator prior to release of subject from study site.
- Any remaining diluted investigational product should be discarded.

If an infusion related reaction is observed, at any time during the ublituximab treatment, the treating investigator may reduce the infusion flow rate at their discretion.

6.2.2.2 FLOW RATE RECOMMENDATIONS FOR UBLITUXIMAB ADMINISTRATION

Cycle 1 infusion over 4 hours

Cycle 1	Ublituximab Dose	Total volume to be infused	Infusion rate			
			T0 to T30'	T30' to T1H	T1H to T2H	T2H to T4H
Day 1	900 mg	500 mL	10 mL/H	20 mL/H	85 mL/H	200 mL/H

Cycle 1 Day 8 & 15 infusions over 3 hours

Ublituximab Dose	Total volume to be infused	Infusion rate		
		T0 to T1H	T1H to T2H	T2H to T3H
900 mg	500 mL	50 mL/H	150 mL/H	300 mL/H

Cycle 2 and remaining infusions over 90 minutes

Ublituximab Dose	Total volume to be infused	Infusion rate	
		T0 to T30min	T30min to T90min
900 mg	500 mL	200 mL/H	400 mL/H

6.2.2.3 DISPENSING OF UBLITUXIMAB

Before dispensing, the site pharmacist or his/her representative must check the ublituximab vial to make sure it is in accordance with the product specifications and that the validity is within the re-test date.

The exact dose of ublituximab as well as the date and time of administration must be recorded within the eCRF, the subject's medical records, and/or in the drug accountability records.

The pharmacist or his/her representative should record all ublituximab drug dispensations in the drug accountability log. When doing this, the complete record should be logged. This includes the subject number, subject initials, date of dispensation, and lot number of the individual vial.

Preparation should be done by the Pharmacist or his/her representative according to instructions for sterile dilution.

6.2.2.4 DILUTIONS OF UBLITUXIMAB

Ublituximab should not be mixed with other medicinal products. Ublituximab should only be diluted in 0.9% NaCl before use. [REDACTED]

Dilutions for ublituximab infusions for vials that contain 6 mL (25 mg/mL)

Dose of ublituximab for infusion	[REDACTED]
900 mg	[REDACTED]

6.2.3 CRITERIA FOR ONGOING TREATMENT

Continue treatment as per protocol provided that subject has:

- No intolerable toxicities related to study drug.
 - Treatment may be delayed to recover from toxicity
- No clinical or radiographic evidence of disease progression.
- Not withdrawn from the study for other reasons.

6.3 DOSING DELAYS AND MODIFICATIONS

Subjects should be assessed clinically for toxicity at each visit using the NCI CTCAE v4.0 (<http://evs.nci.nih.gov/ftp1/CTCAE>) grading scale. Dosing will occur only if a subject's clinical assessment and laboratory test values are acceptable.

At the discretion of the Investigator, a dose re-escalation may be permitted for subjects who were dose reduced upon resuming umbralisib. Subjects that require dose reduction for events that are life-threatening should not be re-escalated. On second dose reduction for the same event contact the Medical Monitor prior to dose re-escalating to discuss management of the subject.

Holidays from study drug are discouraged. However, for subjects requesting a drug holiday without an adverse event, a holiday may be permitted at the discretion of the Investigator. The subject must be on study drug for 3 months to be eligible for a holiday from study drug >4 weeks.

Any subject in whom similar toxicity recurs at the reduced dose should be discontinued from further umbralisib treatment. Exceptions to this discontinuation rule on the basis of ongoing clinical benefit and acceptable/minimal clinical risk may be allowed following a careful assessment and discussion of risk versus benefit with the subject by the Investigator and with approval from the Medical Monitor.

If a subject discontinues only one study drug, the subject may continue treatment with the other study drug per the protocol. Please see Sections 6.3.1 and 6.3.2 below for specific guidelines regarding dose delay and/or modifications. Contact the sponsor prior to discontinuing any study drug(s).

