**Supportive Care – Aggressive management of lipid, glucose, other metabolic disorders, viral infections, etc. Important: Before initiating steroids, check for viral hepatitis or CMV infection.

STUDY DRUG DOSE REDUCTION RECOMMENDATIONS

Study Drug	Starting Dose	1 st Dose Reduction	2 nd Dose Reduction
Umbralisib	800 mg	600 mg	400 mg

A maximum of two dose level reductions are allowed for umbralisib.

If a subject requires a dose reduction of umbralisib due to study drug related toxicity, the dose may not be re-escalated. If further evaluation of the toxicity reveals the event was not related to umbralisib, this must be recorded in the medical record and dose re-escalation to the next higher dose level may be considered at the discretion of the investigator.

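### Sections 6.3 and 6.3.1 (with Table 2) conflict on umbralisib re-escalation and on recurrence at a reduced dose, and no text says which governs

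*Combined protocol and SAP*

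**What the plan says.** **Re-escalation, Section 6.3.** The general rule is permissive: "At the discretion of the Investigator, a dose re-escalation may be permitted for subjects who were dose reduced upon resuming umbralisib". One class is excluded, by severity and without regard to cause: "Subjects that require dose reduction for events that are life-threatening should not be re-escalated". A further step applies to repeat reductions: "On second dose reduction for the same event contact the Medical Monitor prior to dose re-escalating to discuss management of the subject".

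**Re-escalation, Section 6.3.1, below the dose-reduction table.** The general rule is restrictive and turns on cause: "If a subject requires a dose reduction of umbralisib due to study drug related toxicity, the dose may not be re-escalated". It reopens on one condition, "If further evaluation of the toxicity reveals the event was not related to umbralisib", in which case this is documented and "dose re-escalation to the next higher dose level may be considered at the discretion of the investigator". Severity is not mentioned.

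**Recurrence, Section 6.3.** "Any subject in whom similar toxicity recurs at the reduced dose should be discontinued from further umbralisib treatment". Exceptions require a risk-benefit assessment discussed with the subject, and may be made only "with approval from the Medical Monitor".

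**Recurrence, Table 2 in Section 6.3.1.** The Grade 2 row for pulmonary events requires subjects with Grade 1 or 2 pneumonitis to restart one level down. If the event returns after re-challenge, it moves the subject down one more level at the investigator's discretion. The Grade 3 or higher diarrhea row allows the first restart at full dose or one level down, and on recurrence also moves down a level at the investigator's discretion.

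Section 6.3 refers the reader to Sections 6.3.1 and 6.3.2 for detailed guidance. It does not say which text prevails if they differ.

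**The concern.** The two sections decide the same question on different criteria: Section 6.3 looks at severity, Section 6.3.1 at relatedness. Rules built that way cannot agree everywhere unless one is made subordinate to the other, and neither is.

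For recurrence, the texts differ in both the default action (stop, or continue one level lower) and the person who decides (Medical Monitor, or investigator alone). Section 6.3 asks sites to contact the sponsor before discontinuing a study drug, so that duty would not catch a site that resumes dosing under Table 2.

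What is at stake is subject safety. Pneumonitis, where the recurrence clash is most direct, is one of the four toxicities that define unacceptable toxicity in the safety run-in (Section 4.2).

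**Working it through.** The plan gives no figure on this point and no arithmetic is needed beyond counting table rows. The check sets the passages side by side.

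**Step 1: re-escalation after a first reduction.**

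| Event behind the reduction | Section 6.3 | Section 6.3.1 | Result |
|---|---|---|---|
| Related to umbralisib, not life-threatening | Allowed, investigator decides | Barred | Direct clash |
| Related to umbralisib, life-threatening | Barred | Barred | Agree |
| Later judged unrelated to either drug, not life-threatening | Allowed, investigator decides | Can be considered, investigator decides | Agree |
| Later judged unrelated to umbralisib, life-threatening | Should not occur | Can be considered; silent on severity | Ambiguous |
| Related to ublituximab only | Decided by severity alone | First sentence bars it (any study drug); second reopens it (not umbralisib) | Ambiguous within 6.3.1 itself |

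**Step 2: re-escalation after a second reduction for the same event.** Section 6.3 requires contact with the Medical Monitor first. Section 6.3.1 has no such step. So even in the third row of the table, where the outcome agrees for a first reduction, the procedure differs for a second.

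**Step 3: which Table 2 rows conflict with the Section 6.3 recurrence rule.** A row conflicts at the first recurrence only if it allows or requires a reduced restart and also gives a dose instruction on recurrence.

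- Table 2 has 15 rows; 8 give a dose instruction on recurrence.
- 2 of those 8 also provide for a reduced first restart: pulmonary Grade 2 and diarrhea Grade 3 or higher.
- The other 6 do not. For example, Grade 4 neutropenia and Grade 4 thrombocytopenia restart at full dose, and Grade 3 neutropenia continues at the current dose. A first recurrence there is not at a reduced dose.
- 3 further rows (pulmonary Grade 3 or higher, colitis, and the liver row printed as above Grade 3) restart lower but give no dose instruction on recurrence, so nothing in them opposes Section 6.3.

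**Step 4: how firm the conflict is in the two rows.**

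- Grade 1-2 pneumonitis: the reduced restart is mandatory, so any recurrence after re-challenge at that level is at a reduced dose. If it recurs at Grade 1-2, the clash is direct. If it recurs at Grade 3 or higher, Table 2 itself requires discontinuation, in line with the Section 6.3 default.
- Other Grade 2 pulmonary events and Grade 3 or higher diarrhea: the clash arises only if the first restart was at the lower level.

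**Step 5: one case traced through.** The dose levels in Section 6.3.1 are 800, 600 and 400 mg. A subject on 800 mg has Grade 2 pneumonitis and restarts at 600 mg. It recurs at Grade 2. Section 6.3: discontinue, unless the Medical Monitor approves an exception. Table 2: 400 mg, at the investigator's discretion. The limit of two reductions does not settle the matter. It is compatible with both texts, since a second reduction could be for a different toxicity or follow an approved exception.

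**The case against.** The strongest reply is that nobody is forced to breach either text. Where the re-escalation rules differ, one side only permits and the other restricts, so a site that always takes the stricter reading complies with both. On recurrence, stepping down with Medical Monitor approval also satisfies both. Table 2 is labelled as guidance, and Section 6.3 presents Section 6.3.1 as the more specific text.

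Part of this stands. The life-threatening, unrelated case is best called an ambiguity: it rests on Section 6.3.1 being silent on severity, and the express limit in the parent section may well have been meant to carry over.

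The rest does not remove the problem. No passage tells sites to apply the stricter rule, and doing so means setting aside an express permission. Treating Section 6.3.1 as controlling leads elsewhere: it would displace both the discontinuation default and the Medical Monitor's approval when pneumonitis recurs. The reply shows that a careful site could find a compliant path, not that the protocol points to one.

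Three stronger readings are tempting and should not be drawn. A reader might infer from a grid of relatedness by severity that the sections contradict each other in half of all cases. Such a grid counts case types rather than subjects, covers only first reductions and has no cell for ublituximab-only events; only one of its cells is a direct clash. A reader might infer that every pneumonitis recurrence leads Table 2 to a further reduction; at Grade 3 or higher it does not. And a reader might infer measurable between-site variation in the exposure summary (Section 9.6) or in the tabulation of events leading to discontinuation (Section 10.4). Those outcomes already reflect wide investigator discretion, and the documents give no basis for sizing any addition.

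**Conclusion.** The conflict is real but narrower than a general contradiction. There are two direct clashes: re-escalation after a drug-related, non-life-threatening event, and recurrence of Grade 1-2 pneumonitis at Grade 1-2 after its mandatory reduced restart. There are two ambiguities in re-escalation (life-threatening but unrelated to umbralisib; related to ublituximab only), one mismatch in the Medical Monitor contact step after a second reduction, and conditional conflicts for other Grade 2 pulmonary events and for Grade 3 or higher diarrhea.

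This rests on the wording alone and on the absence of any precedence statement. How many of the up to 50 subjects would be affected cannot be derived from the documents, and no effect on the overall response rate is claimed. The point should be fixed because it bears on subject safety and the remedy is cheap. No view is taken on which rule is clinically right.

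**What to change.** Reconcile Sections 6.3 and 6.3.1, including Table 2, into:

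- one re-escalation rule that covers relatedness to each study drug separately, life-threatening status, and second reductions for the same event;
- one rule for toxicity that recurs at a reduced dose, with the Table 2 rows for Grade 2 pulmonary events and Grade 3 or higher diarrhea worded to match;
- a statement of which text governs if they differ, and who approves exceptions.

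The sponsor's medical team decides the content of each rule. The cost is a protocol wording amendment and communication to sites; sample size and study procedures do not change.
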